#### **14.9 Source Document Requirements**

The Investigator will maintain adequate and accurate records for each patient treated with IMP. Source documents including but not limited to hospital, clinic or office charts, laboratory reports, radiology and pathology reports, pharmacy records, study worksheets, anonymized photographs aimed at documenting study-associated clinical findings, and signed ICFs, must completely reflect the nature and extent of the patient's medical care, must be included in the Investigator's files along with patient study records, and must be available for source document verification against entries in the CRF.

Each trial site will permit authorized representatives of the Sponsor and relevant Health Authorities direct access to (and when required by applicable law, to copy) clinical records for the purposes of quality assurance reviews, audits, and evaluation of the trial safety and progress. The Sponsor (or designee) will check CRF entries against source documents according to the guidelines of ICH E6(R2) GCP. Data not requiring a separate written record, i.e., data which may be recorded directly in the CRF, will be determined before trial start.

The ICF will include a statement by which patients allow the Sponsor (or designee), as well as authorized regulatory agencies, to have direct access to source data that support data in the CRF

(e.g., patient medical files, appointment books, original laboratory records, etc.). The Sponsor (or designee), bound by confidentiality and privacy regulations, will not disclose patient identities or personal medical information.

#### **14.10 Laboratory Reports**

Prior to initiation of this study, the Investigator must supply the Sponsor (or designee) with the normal laboratory values for the laboratories to be utilized; specifically, the normal laboratory values for analytes required to be measured, per protocol, are to be supplied.

Laboratory safety evaluations must be performed at the intervals specified. If unexplained laboratory abnormalities occur, corroborative tests will be performed until the laboratory abnormality has resolved, returned to baseline status, and/or adequate explanation of the abnormality has been provided.

Copies of any additional records pertinent to the study (e.g., laboratory data, radiological reports, patient chart summaries, autopsy reports) must be made available to the Sponsor (or designee) or governing Health Authorities, if requested, with due precaution taken to ensure patient confidentiality.

#### **14.11 Record Retention**

Regulatory authorities require that the Investigator retain copies of all files pertaining to the study according to local requirements. In addition, the Investigator is responsible for archiving all relevant source documents so that trial data may be compared against source data after completion of the trial, e.g., in case of inspection from authorities. Study records must be stored in a safe and secure location permitting timely retrieval, if necessary. The Investigator must obtain written permission from the Sponsor prior to disposing of any records.

If the Investigator relocates, retires, or withdraws for any reason from the study, trial records may be transferred to an acceptable designee, such as another Investigator within the institution. The Sponsor (or designee), as well as the responsible IRB/EC, must be notified of the identity of the individual assuming responsibility for maintaining the study records and the location of their storage.

#### **14.12 Monitoring of the Study**

The Sponsor has responsibility to governing Health Authorities to take all reasonable steps to ensure the proper conduct of the study with respect to trial ethics, protocol adherence, and data integrity and validity.

This study will be closely monitored by representatives of the Sponsor (and/or designee) throughout its duration. Monitoring will be in the form of periodic personal visits with the Investigator and his/her staff as well as any appropriate communications by telephone, telefax, mail, or e-mail transmission. The purpose of these contacts is to review study progress, Investigator and patient adherence to protocol requirements, and any emergent problems associated with the conduct of the study. The following usually will be assessed during monitoring visits at the site:

- Required regulatory documentation

- Signed ICFs
- Patient accrual and follow-up
- IMP inventory records
- Investigator and patient compliance to the study protocol
- Concomitant therapy usage
- AE documentation
- Data is accurate, complete, and verifiable when compared to source documents

The Investigator and study staff are expected to cooperate with monitors during such visits and provide them with all relevant study documents. The Investigator must give the Sponsor (and/or designee) direct access to all relevant source documents to confirm consistency with the CRF entries. It is important that the Investigator and relevant personnel are available during monitoring visits and possible audits and that sufficient time is devoted to the process.

In addition, the study may be evaluated by Sponsor auditors (and/or designees) and government inspectors who must be allowed access to CRFs, source documents, and other study files. Sponsor reports will be kept confidential. The Investigator should promptly notify the Sponsor of any audits scheduled by any regulatory authorities, and promptly forward copies of audit reports.

As applicable, in accordance with the Health Insurance Portability and Accountability Act (HIPAA) and associated privacy regulations, patient authorization to use personally identifiable health information may be required from each patient before research activities. This authorization document must clearly specify what parties will have access to a patient's personal health information, for what purpose, and for how long.

#### **14.13 Patient Confidentiality**

Every effort will be made to maintain the anonymity and confidentiality of patients during this clinical study. Each participating site will maintain appropriate medical and research records for this trial, in compliance with ICH E6(R2) GCP, regulatory, and institutional requirements for the protection of confidentiality of patients.

Coded patient identifiers will be utilized always (including in any publications) when referring to a patient. However, because of the experimental nature of this treatment, the Investigator agrees to allow representatives of the Sponsor (and/or designee), as well as authorized representatives of the governing Health Authority, to inspect the facilities used in this study and to inspect, for purposes of verification, the hospital or clinic records of all patients enrolled into this study. A statement to this effect should be included in the ICF.

#### **14.14 Financing and Insurance**

The study will be supported by the Sponsor. Specifics of the financing and insurance coverage will be addressed in the clinical study agreement between the Sponsor and the Investigator or Institution.

## 15 HANDLING AND PROCESSING OF DATA

### 15.1 Data Handling

Study data collection, processing, transfer, and reporting, as well as handling of study personnel information, will be done in compliance with ICH E6(R2) GCP and all applicable data protection regulations, including Regulation (EU) 2016/679 of the European Parliament and of the Council of 27 April 2016 on the protection of natural persons with regard to the processing of personal data and on the free movement of such data (General Data Protection Regulation).

### 15.2 Data Review During this Study

Data obtained from the study will be reviewed in a timely manner throughout by the Sponsor (or designee) and Sponsor's Medical Representative(s) to assess safety and the progress of the project.

### 15.3 Data Processing

A Data Management Plan (DMP) will be prepared for this trial. The Sponsor (or designee) will be responsible for data processing in accordance with applicable Data Management SOPs and the trial DMP.

Once recorded within the CRF, study data will be checked to identify inconsistencies and other data errors, and also will undergo an additional study-specific data review process, as stated above in **Section 15.2**. Data issues will be queried and query resolutions will be documented.

Entry and processing of data other than those directly recorded on CRFs by trial sites (e.g., imports of laboratory results) will follow vendor(s) SOPs. Transfer of such data from vendor(s) to Sponsor (or designee) will be handled according to vendor(s) data transfer SOPs and the Sponsor data transfer requirements with full compliance to applicable regulations.

Database Lock will occur upon reaching the predefined data cut-off and completion of Sponsor's (or designee's) quality control procedures and quality assurance procedures.

Portable Document Format (PDF) files of the CRFs will be provided to the Investigator at the end of the trial.

### 15.4 Clinical Trial Report

**As of Amendment 5:** Due to the Sponsor's decision to discontinue the trial for administrative reasons (effective 20Dec2018), the primary, secondary, and exploratory objectives as previously described are no longer applicable. Only clinical safety-related evaluations will be conducted. An abbreviated CTR will be prepared upon completion of the trial rather than the full integrated report described below.

A final integrated clinical/statistical trial report will be prepared upon reaching the predefined data cut-off for primary analysis (i.e., all patients complete their first on-study tumor assessment).

### 15.5 Compliance with the General Data Protection Regulation

The applicable data protection legislation requires that parties enter into a written contract if one party (data processor) processes personal data on behalf of the other party (data controller). This

written contract must regulate the subject-matter and duration of the processing, the nature and purpose of the processing, the types of personal data and categories of data subjects, as well as the obligations and rights of the data controller. Accordingly, the parties must enter into a data processing agreement. To the extent the processing of personal data involves transfers of personal data to third countries (e.g., jurisdictions outside of the European Economic Area [EEA]), the parties will enter into the European Commission's standard contractual clauses between the data controller, the data processor, and all sub-processors, if any. The European Commission's standard contractual clauses ensure an adequate level of protection in relation to transfers of personal data to third countries.

## 16 STATISTICAL ANALYSIS

### 16.1 Statistical Analysis Plan

A Statistical Analysis Plan (SAP) that includes a more technical and detailed description (including templates for Tables, Listings, and Figures) of the planned statistical summaries analyses will be prepared and finalized prior to database lock.

Further data-driven and exploratory analyses may be defined and performed and presented in the CTR as appropriate.

### 16.2 Sample Size Considerations

**As of Amendment 5:** Effective 20Dec2018, accrual to this trial has been halted; the total planned number of patients will not be enrolled. Two (2) patients consented prior to the trial discontinuation date and subsequently determined to be eligible have been entered to the study. The pre-Amendment 5 sample size considerations detailed below are no longer valid.

Based on Phase 1 and Phase 2 study results, 37-40% of patients receiving Sym004 9/6 mg/kg weekly treatment are expected to have tumor shrinkage at Week 8 (EOC2). With no knowledge of the anti-cancer effect of futuximab and modotuximab, up to 18 patients per Arm may be enrolled and treated to differentiate the rates of 35% versus 10% using a Simon's 2-stage Minimax design, with a 5% significance level and 80% power, for each of the futuximab and modotuximab Arms. In Stage 1, 11 patients will be enrolled in each Arm and treated. If no more than 1 patient has tumor shrinkage in an Arm, further enrollment will be stopped in that Arm. Otherwise, an additional 7 patients will be enrolled in Stage 2.

A contemporary reference Sym004 Arm will be included in the study to ensure the interpretability of tumor shrinkage data for the Futuximab Arm and Modotuximab Arm.

If either of the Futuximab or Modotuximab Arms continues in Stage 2 or beyond, the Sym004 Arm enrollment will continue.

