#### Criteria for Evaluability

[figure not shown]
To be considered evaluable for antitumor activity assessment, patients must have completed 2 cycles of dosing inclusive of EOC2 disease imaging studies (i.e., computed tomography [CT]/magnetic resonance imaging [MRI]), and must have received any amount of their assigned investigational medicinal product (IMP) during that period, or have PD documented by imaging studies prior to the EOC2. Nonevaluable patients and patients discontinuing from study prior to the EOC2 due to either documented PD or for reasons other than documented PD will not be replaced (*every effort will be made to obtain imaging studies at the time of discontinuation*).

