#### 4.1.2 Planned Sample Size

Up to approximately 54 evaluable patients (18 evaluable patients per Arm)

Note: To be considered evaluable for antitumor activity assessment, patients must have completed 2 cycles of dosing inclusive of EOC2 disease imaging studies and must have received at least 6 of 8 doses of their assigned IMP during that period or have PD documented by imaging studies prior to the EOC2. Non-evaluable patients and patients discontinuing from study prior to the EOC2 due to either documented PD or for reasons other than documented PD, will not be replaced.

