#### 6.2.2 Trial Duration

**As of Amendment 5:** Due to the Sponsor's decision to discontinue the trial (effective 20Dec2018), the primary, secondary, and exploratory objectives as previously described are no longer applicable. Planned efficacy analyses, as well as planned specialty analyses (including ADA as well as exploratory PK and PD analyses) will not be performed. Only clinical safety-related analyses will be conducted; data cut-off will occur and safety analyses will be performed at the end of trial.

Data Cut-off for Primary Analysis: When the required number of evaluable patients (18 patients per Arm) have been treated for a minimum of 2 cycles, have received any amount of their assigned IMP during that period, and have either undergone EOC2 imaging studies or have had PD documented by imaging studies prior to the EOC2, the trial objectives will be considered to have been met. That date will be the data cut-off date for the primary analysis.

Patients still in treatment will be given the opportunity to continue receiving Sym004.

Data Collection beyond Primary Analysis: While the Sponsor still needs to collect certain safety-related data to meet its regulatory obligations (AEs, serious adverse events [SAEs], IMP dosing, reason for discontinuation, etc.), the Sponsor may elect to reduce non-safety-related protocol-stipulated assessments, and/or transition patients to an extension/rollover protocol.

End of Trial: The end of trial will be reached at the latest 1 month (30 +7 days) after the last patient has been discontinued from study drug.

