## 9.2 Replacements

After randomization to the study, no patients will be replaced. Patients NE for antitumor activity assessment, as defined (**Section 3.2**), or patients discontinuing from study prior to the EOC2 due to either documented PD or for reasons other than documented PD, will not be replaced.

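### Does the 80% power for each single-agent arm fail because 18 patients are enrolled, none is replaced and evaluability is defined two ways?

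*Protocol*

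**What the plan says.** Section 16.2 of the protocol plans a Simon two-stage Minimax design in which "up to 18 patients per Arm may be enrolled and treated to differentiate the rates of 35% versus 10" per cent, "with a 5% significance level and 80% power, for each of the futuximab and modotuximab Arms". The first stage is fixed: "In Stage 1, 11 patients will be enrolled in each Arm and treated. If no more than 1 patient has tumor shrinkage in an Arm", enrolment to that arm stops. Otherwise 7 more patients are added, giving 18. The final success boundary is not printed.

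Other sections count differently. Section 4.1.2 gives the planned size as "Up to approximately 54 evaluable patients (18 evaluable patients per Arm"). Section 6.2.2 sets the primary data cut-off at the point "When the required number of evaluable patients (18 patients per Arm) have been treated for a minimum of 2 cycles" and have been imaged. Section 9.2 adds: "After randomization to the study, no patients will be replaced".

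The dose condition for being evaluable also differs. The note in Section 4.1.2 says patients "must have received at least 6 of 8 doses of their assigned IMP during that period". Section 3.2 says they "must have received any amount of their assigned investigational medicinal product (IMP) during that period", and the synopsis and Section 6.2.2 agree with Section 3.2. Under every version, progression documented by imaging before the end of Cycle 2 makes a patient evaluable.

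Amendment 5 notices sit above most of this text. The one in Section 16.2 states that the sample size considerations are no longer valid.

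**The concern.** A Minimax design uses the smallest total that meets its error limits, so it has nothing to spare. If 18 is the most that can be enrolled and nobody is replaced, then 18 evaluable patients are obtained only when no patient is lost. No allowance for loss is stated. One missing scan would put an arm below the number behind the 80%.

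Two further points add to this. A patient with five doses and an end-of-Cycle-2 scan is evaluable under Section 3.2 and not under Section 4.1.2, so the same data could give two shrinkage rates. The Section 6.2.2 cut-off, read literally, would never be reached if one patient were non-evaluable or if an arm stopped after 11.

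Had the trial run as first designed, the go or no-go decision for futuximab and modotuximab would have rested on a power figure that could be several points too high, and on a denominator open to choice.

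**Working it through.** **Inputs from Section 16.2:** null rate 10%, target rate 35%, first stage 11 patients, stop if at most 1 shows shrinkage, second stage 7 patients, significance level 5%, power 80%. The significance level is taken as one-sided, as is usual for a Simon design.

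**Formula.** With final boundary r (success if more than r of 18 shrink), the chance of declaring an arm active at true rate p is

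Σ over x from 2 to 11 of P(Bin(11, p) = x) × P(Bin(7, p) ≥ max(0, r + 1 − x)).

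**Finding the boundary.** At r = 3 the type I error is 0.0875, which is too high. At r = 5 the power is 0.642, which is too low. Only r = 4, success with at least 5 of 18, meets both limits.

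**Reproducing the stated figure at r = 4:**

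| First-stage shrinkers | p = 0.35 | p = 0.10 |
|---|---|---|
| 2 (needs ≥ 3 of 7) | 0.1396 × 0.4677 = 0.0653 | 0.2131 × 0.0257 = 0.0055 |
| 3 (needs ≥ 2 of 7) | 0.2254 × 0.7662 = 0.1727 | 0.0710 × 0.1497 = 0.0106 |
| 4 (needs ≥ 1 of 7) | 0.2428 × 0.9510 = 0.2309 | 0.0158 × 0.5217 = 0.0082 |
| 5 or more | 0.3317 | 0.0028 |
| Sum | **0.8005** (power) | **0.0271** (type I error) |

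The 18 patients and the 80% reproduce. An exhaustive search finds no two-stage design with fewer than 18 patients that meets both limits. The slack on power is 0.05 percentage points.

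**Fewer evaluable patients, first stage kept at 11:**

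| Evaluable | Power, ≥ 5 needed | Type I error, ≥ 5 needed | Type I error if only ≥ 4 needed |
|---|---|---|---|
| 18 | 80.05% | 2.7% | 8.7% |
| 17 | 75.9% | 2.2% | 7.6% |
| 16 | 70.8% | 1.7% | 6.5% |
| 15 | 64.7% | 1.3% | 5.4% |

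Type I error exceeds 5% only in the last column, and the protocol nowhere proposes that lower boundary.

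**Loss counted as no shrinkage among 18 treated.** The target rate becomes 0.35 × (1 − d), where d is the non-evaluable share. The protocol gives no value of d for this trial, so these are assumptions:

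- d = 2%: power 78.3%
- d = 5%: power 75.5%; chance that an arm loses at least one patient 1 − 0.95^18 = 60%
- d = 6%: power 74.5%
- d = 10%: power 70.4%; chance of at least one loss 1 − 0.90^18 = 85%

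The nearest figure in the protocol is in Section 2.4.1: 6.0% of patients on Sym004 9/6 mg/kg in the earlier Phase 2b trial stopped treatment for adverse events. It covers the whole treatment period and another product, so it is only a rough guide.

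**What Amendment 5 leaves in force:**

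| Pre-amendment element | Amendment 5 position |
|---|---|
| Sample size and power (16.2) | no longer valid |
| Efficacy endpoint (16.4) | will not be analyzed |
| Efficacy analysis (16.6) | will not be performed |
| Stage 1 and Stage 2 evaluations (16.10) | will not be performed |
| Cut-off at 18 evaluable per arm (6.2.2) | cut-off at end of trial |
| Summaries by arm (16.5) | profiles or listings for 2 patients |

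Both patients were randomized to futuximab. Section 6.5.4 records that one crossed over to Sym004 at the end of Cycle 1 and the other received Sym004 from entry.

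**The case for a change.** The best case for a change is that the contradictions need no assumption to be seen. Eighteen enrolled and eighteen evaluable agree only with zero loss, the two dose conditions cannot both hold, and the Section 4.1.2 note has no correction of its own. The protocol still prints this design, and reconciling it would cost only wording.

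Much of this is right as a description, but four points reduce its weight.

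- Section 16.2 counts patients enrolled and treated and gives the expected Sym004 rate per patient receiving it. Section 16.3 makes the As-Treated set the basis for antitumor effects. If 10% and 35% are rates per treated patient, 18 treated patients deliver 80.05% without inflation. This does not settle the matter, because Section 16.5.1 leaves missing data unimputed and no section says which denominator governs the 11 + 7 decision.
- Section 16.5.1 gives another cut-off, when all As-Treated patients have had their first on-study tumor assessment. It needs neither 18 evaluable patients nor a completed second stage. The protocol therefore holds two cut-off rules, one of which can be met.
- Early progression on imaging counts as evaluable, so only other losses matter. The size of the shortfall rests on an assumed rate.
- Section 9.2 refers to Section 3.2 for the evaluability definition, so an analyst would see that the Section 4.1.2 note is the outlier. The Amendment 5 notice at the head of Section 4.1 covers that subsection, although it speaks only of site and patient numbers.

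**Conclusion.** No change is needed, because a change would gain nothing. The stated design is computed correctly: 18 patients per arm give 80.05% power and 2.7% type I error. The text around it is loose. It mixes enrolled with evaluable patients, carries two dose conditions for evaluability and gives two cut-off rules. In a running trial the first of these could have cost about 4 points of power for one lost patient (80.05% to 75.9%), or about 5 to 10 points under an assumed 5% to 10% loss counted as no shrinkage. Type I error would not have suffered with the boundary kept at 5 of 18.

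None of this can now have an effect. Amendment 5 withdraws the sample size basis, cancels every analysis that would use the evaluable set or the two-stage boundary, and replaces the cut-off. Two patients remain, both on Sym004 and reported individually. The mismatches are an editorial matter in superseded design text. This conclusion depends on Amendment 5 standing; if the design were reused in another trial, the evaluability definition and the denominator behind the power would have to be reconciled first.
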